6.2.2 Secondary outcome

Secondary outcomes are death due to bleeding if available in the registry, early death (< 24 hours) and coagulopathy at hospital admission defined by an INR > 1.2 or TP $< 70\%$ or Fibrinogen ≤ 1.5 g/L (each other will be used for sensibility analysis)^{7,8,9}.

5.2. Analysis methods

5.2.1. Efficacy analyses of primary outcome

First, the investigators will assess the accuracy (overall performance), discrimination and calibration of ABC, TASH and BATT score for the prediction of massive transfusion in trauma patients at the trauma scene and at the hospital admission.

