
Measurements and procedures:
	
Predictive Variables:
 
Demographics: Age, gender, type of accident, mechanism of Injury (penetrating/blunt), Hospital (anonymised by number), Date and time of accident.
 
Prehospital settings: Arrival on scene (paramedics, date/time and medics, date/time), type of transport: physician staffed ambulance/helicopter, Firsts clinical measures recorded: Systolic blood pressure (SBP), Respiratory rate (RR), Heart Rate (HR), Pulse Oximetry, Glasgow coma scale, temperature, cardiopulmonary reanimation, Drugs Use: Tranexamic acid (Date/time) and vasoactive, early death before arriving to the hospital.
 
In-hospital settings (trauma room): Hospital arrival (date/hour), Firsts measures: Systolic blood pressure (SBP), Respiratory rate (RR), Heart Rate (HR), Pulse Oximetry, Glasgow coma scale, temperature, cardiopulmonary reanimation, Biological parameters: haemoglobin, Platelets, lactates, Base excess, TP (sec and %), INR, PTT, Fibrinogen, Drugs use: Tranexamic acid (date/time), vasoactive, Vitamin K, Fibrinogen, Prothrombin complex concentrate, rFVIIa, Red blood cell (number in the first hour, date/hour of each Red blood cell), platelets units, fresh frozen plasma.
 
Imaging: type of imaging, results: positive or negative for free fluid, date/time of imaging.
 
Diagnosis: AIS final, ISS final, Medical past, use of anticoagulant/antiaggregant before trauma
 
Outcome: Date/time of death, Early death (<12 hours), Early death (<24 hours), number of red blood cell in 24 hours, Massive transfusion (defined as ≥ 10 red blood cells in the first 24 hours).
 
Depending of the availability of requested variables in the registry, we will ask for complementary variables.
 
Comparison:
 
Performance comparison of pre-existing scores (TASH, ABC and BATT scores) in term of overall performance, discrimination and calibration.
 
Evaluation of clinical utility and feasibility in prehospital settings and emergency admission.

Intervention:
	
Comparison of score performances (Overall performance, discrimination and calibration)

Control Intervention (if applicable):
	
No group controls

Number of Participants with Rationale:
	
The number of participants will depend of the Swiss Trauma Registry Database. We project to include 10'000 participants for our study. A post-hoc power calculation will be performed.

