2.1 Background and rationale

Since the 2000s, many prognostic scores were developed to predict traumatic haemorrhage. Most of these studies were retrospectives based on registers. Due to missing data on death due to bleeding, these studies chose to predict the massive transfusion risk as a surrogate of haemorrhagic death. These scores include clinical parameters (vital signs), laboratory values (Haemoglobin, lactate, Base excess) and/or imaging (CT or ultrasound) values. The scores showing best performance are the Trauma Associated Severe Haemorrhage (TASH) score, developed and validated on the German register (DGU-Register) (1, 2) and the ABC score developed and validated in the United States of America (3, 4). The scores with variables are described on Figure 1,2.

However, the majority of these scores cannot be applied at the trauma scene due to the unavailability of laboratory and imaging values. Therefore, their clinical utility remains unclear. To overcome the need for diagnostic tests, authors have developed and recently validated a clinical prognostic score in identifying trauma patients with, or at risk of, significant haemorrhage based on predicted probabilities of death due to bleeding: BATT score (5). This score was developed from an international cohort using data from 271 Trauma Centres in 41 countries on 5 continents and uses first clinical parameters at initial assessment. The BATT score predicts death due to bleeding and has been validated on a large population in England and Wales. It could also predict massive transfusion, as a surrogate of haemorrhagic death, earlier at the trauma scene. Its feasibility and external validation would make its clinical utility superior to other scores while identifying a greater number of patients requiring early management.

Our study is an external validation of pre-existing prognostic scores of traumatic haemorrhages (TASH^{1,2}, ABC^{3,4} and BATT⁵ score) at different times of care (Scene of Injury, admission at the trauma room) in order to assess their overall performance, discrimination and calibration in the prediction of massive transfusion, and haemorrhagic death. The objective of the study is to assess a comparison of score performances (Overall performance, discrimination and calibration).

3. Study Methods

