5.2.3. Discrimination

Discrimination is the ability of the score to correctly identify patients with the outcome. The investigators will estimate the sensitivity, specificity, positive and negative likelihood ratio for the defined threshold of each score (ABC, TASH, BATT).

The likelihood ratio is the likelihood of a positive score in a patient with the outcome compared to the likelihood of a positive score in a patient without the outcome. The positive likelihood ratio is the ratio of sensitivity to 1-specificity. The negative likelihood ratio is the ratio of 1-sensitivity to specificity. A positive likelihood ratio of 10 or above will result in a large increase in the probability of the outcome. A negative likelihood ratio of 0.1 or less will result in a large decrease in the probability of the outcome.

The investigators will plot the Receiving Operating Characteristic (ROC) curve which is the sensitivity (true positives) on 1-specificity (false positives) for each defined threshold of each

score. An ideal score will reach the upper left corner (all true positive with no false positive). The investigators will estimate the area under the ROC curve (AUROC) that corresponds to the concordance statistic (C-Statistic) for binary outcome. A C-statistic of 1.0 shows perfect discrimination ability.

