5.2.4. Calibration

Calibration is the agreement between observed and predicted outcomes. The investigators will mostly estimate calibration as the difference between the mean predicted and observed probabilities and the ratio of the predicted and observed number of events (P/O). The investigators will plot the observed and predicted probabilities of massive transfusion by decile of the score and with local regression based on LOESS algorithm. The investigators will estimate the calibration intercept and slope of the calibration plot as a measure of spread between predicted and observed outcome. Ideally, the intercept would be zero indicating that the predictions are neither systematically too low or too high and the slope would be 1.

Unfortunately, the investigators cannot estimate the calibration of the BATT score, because of its different outcome (death due to bleeding and not the massive transfusion as the TASH and ABC score). For the BATT, calibration will be assessed with the outcome of death due to bleeding or early death.

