5.2.1. Imputation method

To estimate baseline risk for the full dataset, the investigators will replace missing predictors using multiple imputation by chained equations on sex, age, systolic blood pressure, respiratory rate, heart rate, Glasgow coma scale, Haemoglobin, base excess, type of injury (penetrating/blunt) Instable pelvis fracture and open/dislocated femur fracture with 20 imputed dataset. All analysis and results will be present in two subgroups: missing data imputed and missing data excluded.

5.2.2. Early deaths and early deaths with haemorrhage as a proxy for death due to bleeding

Because the investigators don't know if the Swiss Trauma Registry record the cause of death, the investigators expect some missing data about death due to bleeding as a secondary outcome. In case of missing data on secondary outcomes, the investigators will use early deaths and early deaths with evidence of haemorrhage as a proxy for death due to bleeding. Specifically, the investigators will included deaths from all causes within 12 hours of injury (excluding massive destruction of skull or brain; asphyxia, drowning and hanging are already excluded from the STR) and deaths between 12 to 24 hours with evidence of bleeding (Activation of massive transfusion protocol or blood within 6 hours or an abbreviated injury scale (AIS) diagnosis associated with haemorrhage: Blood loss >20%, Aorta [OR] Vena Cava [OR]carotid [OR]femoral [OR]Major arteries [OR]veins AND laceration, - Spleen [OR]liver [OR] Kidney [OR] Myocardium [AND] major laceration, major haemothorax, retroperitoneum haemorrhage).

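### The objective is to compare TASH, ABC and BATT, but the plan specifies no between-score contrast and does not secure a common set of patients for one

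*SAP*

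**What the plan says.** SAP 2.1 (Background and rationale) states: "The objective of the study is to assess a comparison of score performances". The Protocol synopsis (Measurements and procedures) agrees: "Performance comparison of pre-existing scores (TASH, ABC and BATT scores) in term of overall performance, discrimination and calibration".

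For the primary outcome, SAP 5.2.1 (Efficacy analyses of primary outcome) says: "First, the investigators will assess the accuracy (overall performance), discrimination and calibration of ABC, TASH and BATT score". SAP 5.2.2 to 5.2.4 then define the Brier and scaled Brier scores, sensitivity, specificity, likelihood ratios, AUROC and calibration. On discrimination: "The investigators will estimate the area under the ROC curve (AUROC) that corresponds to the concordance statistic (C-Statistic) for binary outcome". On calibration for massive transfusion: "Unfortunately, the investigators cannot estimate the calibration of the BATT score, because of its different outcome". The paragraph on secondary outcomes repeats the same analyses. The Protocol's Statistical Considerations put a comparison heading over a list of per-score measures and refer to the SAP.

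On missing predictors, SAP 5.2.1 (Imputation method) plans chained equations with 20 imputed datasets and adds: "All analysis and results will be present in two subgroups: missing data imputed and missing data excluded". SAP 5.3 repeats this split as Subgroup 5 and calls the second part the complete-case analysis.

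**The concern.** A comparison needs an estimated difference between scores, a measure of its uncertainty, and the same patients on both sides. The plan fixes none of these. SAP section 6 already expects an ordering (TASH to transport well, ABC to discriminate less well, BATT to be clinically more useful if validated), so the report will probably rank the scores. Without a specified contrast, the ranking would be read from AUROCs printed side by side, or from a method chosen after the results are known.

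The patient set matters because the scores need different inputs. If TASH and ABC can be computed only where imaging and other items were recorded, while BATT can be computed more widely, a gap between AUROCs may reflect who was measured and not how well each score works.

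**Working it through.** The documents give no power or precision figure for a comparison, so there is nothing to reproduce. The 10,000 participants in SAP 3.2 are a registry projection.

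**1. Is there a comparative step?** Brier, AUROC, threshold measures and calibration are each defined for a single score. No section of SAP 5 gives a difference, an interval or a paired method. The only heterogeneity test (SAP 5.3, Subgroup 6) is between centres.

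**2. Is the patient set common?**
- TASH (SAP Figure 1) needs haemoglobin, base excess, systolic pressure, heart rate, free abdominal fluid, two fracture items and sex.
- ABC (SAP Figure 2) needs mechanism, systolic pressure, heart rate and FAST.
- The documents do not itemise BATT. SAP section 6 describes it as using only simple physiological variables.
- The imputation list covers sex, age, systolic pressure, respiratory rate, heart rate, GCS, haemoglobin, base excess, injury type and the two fractures. FAST/free fluid is not on it.

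So, even after imputation, TASH and ABC may be uncomputable for patients in whom BATT is available. In the excluded set, the documents do not say whether exclusion is per score or across all three.

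**3. Precision of an AUROC difference.** From the SAP: N = 10,000. Assumed: both AUROCs A = 0.80; massive transfusion 2%, 5% or 10%; correlation r between the two AUROC estimates 0.5 or 0.7.

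Hanley-McNeil: SE² = [A(1−A) + (n₁−1)(Q₁−A²) + (n₀−1)(Q₂−A²)] / (n₁n₀), with Q₁ = A/(2−A) = 0.6667 and Q₂ = 2A²/(1+A) = 0.7111.

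At 5%, n₁ = 500 and n₀ = 9,500: SE² = [0.16 + 499 × 0.02667 + 9,499 × 0.07111] / 4,750,000 = 688.95 / 4,750,000, so SE = 0.01204.

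SE(difference) = SE × √(2(1−r)), and the half-width is 1.96 times that:

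| Events | SE of one AUROC | Independent (r = 0) | Paired, r = 0.5 | Paired, r = 0.7 |
|---|---|---|---|---|
| 200 (2%) | 0.0189 | 0.0525 | 0.0371 | 0.0287 |
| 500 (5%) | 0.0120 | 0.0334 | 0.0236 | 0.0183 |
| 1,000 (10%) | 0.0086 | 0.0239 | 0.0169 | 0.0131 |

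The ratio of independent to paired width is 1/√(1−r): 1.41 at r = 0.5 and 1.83 at r = 0.7.

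**4. Can different patients create a false ranking?** This was checked by simulating 400,000 patients. Two equally good scores each equalled a latent severity plus independent noise (SD 0.7). The outcome followed a logistic model in severity (slope 1.8) at 2%, 5% or 10% prevalence. One score was computable only where FAST was recorded, with 20% or 40% missing and recording related to severity by a logistic slope of 0, 0.5, 1 or 1.5. All of these values are assumptions.
- Different patients, recording related to severity: the AUROCs differed by 0.004 to 0.039. The example at 5% events, 40% missing and slope 1.5 gives 0.816 against 0.777.
- Different patients, recording unrelated to severity: the gap was at most 0.003.
- Same patients: the gap was at most 0.003 in every setting.

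**The case against.** Several points on the other side have weight.

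- **Complete-case sets.** A reader might infer that the complete-case AUROCs will come from different patients. The documents do not say that. The SAP speaks of two subgroups and of one complete-case analysis, and a single set with all predictors complete is a natural reading. What stands is that the plan leaves it open.
- **No primary set.** A reader might also infer that imputed and complete-case results have equal standing. That is too strong. Multiple imputation is the only missing-data method in the Protocol, the SAP imputes to cover the full dataset, and the complete-case analysis reappears among subgroup analyses that depend on sample size. What stands is that the SAP presents both side by side and labels neither as primary.
- **Unpaired design or over-wide intervals.** The design is not unpaired, since every score comes from the same registry patients. Nor does the plan propose intervals that treat the AUROCs as independent; it proposes none. The half-widths therefore show the precision available from pairing, not an error in a planned calculation.
- **The word First.** In SAP 5.2.1 it may mean only primary before secondary outcomes, so it is no evidence of a lost step. The point does not rely on it.
- **Standing of the comparison.** The Protocol lists external validation ahead of comparison. But SAP 2.1 names comparison as the objective, and the Protocol lists it as an objective too.

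Analysts could add a paired test later, but the comparison would then not be prespecified, whereas SAP section 7 says the plan is meant to limit data-driven results.

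**Conclusion.** The concern holds in this form: the comparison named as the objective has no specified analysis, and a common patient set is not secured. The missing contrast follows from the text alone and needs no numerical assumption. The effect of different patients is conditional: it requires per-score exclusion or unimputed FAST/free fluid, and missingness related to severity. Under those conditions the simulated false gap reached about 0.04. It was close to zero when recording was unrelated to severity.

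The precision at stake, at N = 10,000 and AUROC 0.80, is a half-width of 0.033 against 0.024 (r = 0.5) or 0.018 (r = 0.7) at 5% events. From 2% to 10% events it runs from 0.0525 to 0.0239 as independent, and from 0.0371 to 0.0169 paired at r = 0.5. Event rate, AUROC and correlation are assumed, so these figures show scale only. Per-score estimates remain obtainable, so this should be corrected but does not invalidate the study.

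**What to change.** Add a comparative step to SAP 5.2 and adjust the missing-data section:

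1. Add FAST/free fluid to the imputation model so that TASH and ABC can be computed for everyone.
2. In each of the 20 imputed datasets, compute all three scores in the same patients and estimate pairwise AUROC differences with 95% confidence intervals, by DeLong or a paired bootstrap clustered by centre. Pool by Rubin's rules.
3. Label the imputed analysis explicitly as primary.
4. Restrict the complete-case sensitivity analysis to patients with all three scores computable.
5. Limit Brier contrasts to scores that give a predicted probability for the outcome analysed. For massive transfusion the documents give probabilities only for TASH, so little can be contrasted there. State that calibration for massive transfusion is not compared with BATT.

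The cost is a few lines in the SAP, a little more analysis work, and a smaller common complete-case set.

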
Objective(s):
	
 - External validation of pre-existing prognostic scores of traumatic haemorrhages at different times of care (Scene of Injury, admission at the trauma room) in order to assess their overall performance, discrimination and calibration in the prediction of massive transfusion and haemorrhagic death. - Comparison of score performances (Overall performance, discrimination and calibration).

Outcome(s):
	
Primary study outcome :
 
 - Massive transfusion defined by a transfusion equal to or greater than 10 Red blood cell (RBC) / 24 hours or ≥ 3 RBC in the first hour if available in the Swiss Trauma Registry. 
Secondary study outcome :
 
 - Death due to bleeding (if available in the registry) - Early death (< 24 hours) - Coagulopathy at admission defined by INR > 1.2, quick TP < 70% or Fibrinogen < 1.5 g/L (6,7,8)

Study design:
	
Observational non-interventional study based on a multicentric anonymized registry

Inclusion / Exclusion criteria:	
Study population: All adult trauma patients treated at twelve Swiss trauma centres Level I from 01.01.2015 to 31.12.2019 with eligible criteria of the Swiss Trauma Registry (STR) are included. All data from the register are anonymised without any access to medical files. The identity of the trauma patients, date of birth, address and trauma scene location are unknown (as mandatory by the swiss law: Art. 2 ORH).
 
Inclusion criteria:
 
- Age > 16 years old- ISS (Injury Severity Score) ≥ 16 and/or AIS head (Abbreviated Injured scale) ≥ 3 
Exclusion criteria:
 
- Age < 16 years old- ISS < 16 and or AIS < 3- Isolated Burns (including electric shock) or if the burn is clearly the primary injury- Patients arriving at the trauma room with no sign of life and no diagnostic/therapeutic measures have been initiated for them- Choking or hanging patient without any other injury.- Drowning patients
--	---

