4.3 Baseline patient characteristics

4.3.1 *Collected baseline patient characteristics*

The observational study is designed to record a set of demographical data, clinical examination in prehospital or in-hospital setting, in-hospital biochemical values and imaging variables for each included patient. The investigators will extract the data from the Swiss trauma registry (STR). The investigators plan to extract the biological parameters from the register at the trauma room stage. The clinical examinations will be the first measures at the pre and in-hospital stage. **Table 1** provides an overview of all variables requested from the registry before receiving the dataset.

4.3.2 *Descriptive summary of baseline patient characteristics*

The investigators will list general patient characteristics in a baseline characteristics table. Data will be presented as mean with standard deviation (SD) when normally distributed or as median with interquartile range in case of skewed data. Dichotomous and categorical data will be presented in proportions. **Table 2** provides a summary of potential baseline characteristics.

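### TASH and ABC are planned at the trauma scene, but items they need are collected only in the trauma room: no valid scene TASH can be formed as written, and scene ABC is conditionally affected

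*SAP*

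**What the plan says.** The Protocol synopsis (Objectives) announces "External validation of pre-existing prognostic scores of traumatic haemorrhages at different times of care (Scene of Injury, admission at the trauma room"), and SAP 2.1 repeats the two times of care. SAP 5.2.1 (Efficacy analyses of primary outcome) applies this to all three scores: "ABC, TASH and BATT score for the prediction of massive transfusion in trauma patients at the trauma scene and at the hospital admission". In SAP Table 1 the TASH, ABC and BATT rows each carry an X under Prehospital and under In-hospital.

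The inputs are placed differently. SAP 4.3.1 states: "The investigators plan to extract the biological parameters from the register at the trauma room stage". For vital signs it states: "The clinical examinations will be the first measures at the pre and in-hospital stage". Table 1 agrees: heart rate and systolic blood pressure are marked at both stages, haemoglobin and base excess in the trauma-room column only. The Protocol synopsis (Measurements and procedures) also lists "Biological parameters: haemoglobin, Platelets, lactates, Base excess" under the trauma-room heading. Table 1 marks free fluid on CT or FAST in the trauma-room column only. The Protocol gives imaging its own heading, with no setting: "type of imaging, results: positive or negative for free fluid, date/time of imaging".

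SAP 2.1 concedes that "the majority of these scores cannot be applied at the trauma scene due to the unavailability of laboratory and imaging values". SAP Figures 1 and 2 give only the full TASH and ABC. Neither document defines a reduced scene version or a rule for items absent at the scene.

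**The concern.** A score meant to predict at the scene must be built from what is known at the scene. If TASH and ABC are reported there as planned, the analyst has to decide how to fill the items that are collected later, and the SAP does not say how. The decision would then be taken after the data arrive, although the SAP is meant to be fixed before that (SAP 3.3).

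The choice affects the study's central contrast. The SAP Discussion presents BATT as a score that needs only variables available at the scene, and anticipates using it there. If a scene BATT is set beside a so-called scene TASH that contains later laboratory and imaging results, TASH would be expected to gain from that later information. The comparison would then not describe how TASH performs at the scene.

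**Working it through.** **Step 1. Rebuild the plan's own maximum.** Highest points per TASH item in SAP Figure 1, with the stage given in SAP Table 1:

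| Item | Max points | Stage in Table 1 |
|---|---|---|
| Haemoglobin | 8 | trauma room only |
| Base excess | 4 | trauma room only |
| Free abdominal fluid | 3 | trauma room only |
| Systolic blood pressure | 4 | both |
| Heart rate | 2 | both |
| Male sex | 1 | prehospital |
| Unstable pelvic fracture | 6 | no row of its own |
| Open or dislocated femur fracture | 3 | no row of its own |

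Sum: 8 + 4 + 3 + 4 + 2 + 1 + 6 + 3 = 31. This matches the upper TASH band of 18 to 31 in SAP Table 2.

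**Step 2. TASH points missing at the scene.**
- Fracture items assumed known at the scene: 8 + 4 + 3 = 15 missing; 15/31 = 48%; maximum left 31 − 15 = 16.
- Fracture items assumed to come only from AIS codes, which Table 1 marks In-hospital: 15 + 6 + 3 = 24 missing; 24/31 = 77%; maximum left 31 − 24 = 7.

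The documents do not say which case applies, so the range is 15 to 24 points. Even if free fluid and the fracture items were all known at the scene, haemoglobin and base excess would be missing: 8 + 4 = 12; 12/31 = 39%.

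**Step 3. ABC at the scene.** SAP Figure 2 has four one-point items: mechanism, systolic blood pressure, heart rate and FAST. By Table 1 only FAST is missing, so the maximum is 3 and the cut-off of 2 can still be reached. Of the 16 possible item patterns, 11 are positive with FAST and 8 without, so 3 change to negative.

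**Step 4. Ways to fill the missing items.**
- *Complete cases* (SAP 5.3, Subgroup 5). If scene values were required, nobody would be complete for TASH. The SAP does not state that requirement.
- *Imputation* (SAP section Imputation method). Haemoglobin and base excess are on the list without a stage. The only such values requested are from the trauma room, so imputation most naturally fills gaps in those. Free fluid is not on the list.
- *Mixed times.* Scene vital signs are combined with trauma-room laboratory and imaging values, observed or imputed, and with AIS codes if these supply the fracture items. This is the only full scene TASH that can be computed, and it uses information from after the prediction time. Only systolic blood pressure and heart rate would differ from the admission score: 4 + 2 = 6 of 31 maximum points, with 31 − 6 = 25 shared.

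**The case against.** The best defence is that SAP 2.1 already says most such scores cannot be applied at the scene, so the objective can be read as each score at its feasible time. That is a fair reading of the objective, and rewording it is therefore optional. It does not rescue Table 1, which marks TASH and ABC under Prehospital, or 5.2.1, which names both scores at both times.

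The Protocol also leaves room to request further variables and plans to evaluate feasibility in prehospital settings. Neither supplies scene laboratory values nor defines a scene score.

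Table 1 is not a strict map of availability: Subgroup 7 needs prehospital fluid volume, which has no row. This weakens the inference for imaging, where the Protocol states no setting. It does not weaken it for laboratory values, where SAP 4.3.1 and the Protocol agree with the table.

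Three stronger readings are tempting but not supported:
- *That no valid scene ABC is possible.* Timed scene imaging is not strictly excluded, and patients who had it would have a complete ABC.
- *That scene TASH would have zero sensitivity because its maximum of 16 lies below 18.* This needs absent items to be scored as 0, which the SAP does not state, and a cut-off of 18 that is only inferred from the Table 2 bands.
- *That the 25 shared points show how alike the scene and admission results would be.* Shares of maximum points are not shares of score variation or discrimination.

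**Conclusion.** The concern holds with high confidence for TASH and conditionally for ABC. As written, the plan yields either no scene TASH or one that uses information from after the prediction time. The missing share is 15 of 31 points (48%), rising to 24 of 31 (77%) under the assumption that the fracture items come only from in-hospital AIS codes. For ABC, one of 4 items is missing by Table 1, and the score is complete only where FAST was recorded at the scene.

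That a mixed-time TASH would look better than it should beside a scene BATT is an expectation about direction; its size cannot be computed from the documents. A reader might infer that the whole comparison of scores fails. It does not: scene BATT and the comparison of all three scores at admission are unaffected. This should be fixed before analysis.

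**What to change.** 1. In SAP Table 1, remove the Prehospital X for the original TASH. Do the same for the original ABC unless FAST timed at the scene is available.
2. In SAP 5.2.1 (Efficacy analyses of primary outcome) and in Subgroup 4, state that scene analyses use only scores built from data recorded at the scene. State also that trauma-room haemoglobin, base excess, imaging and in-hospital AIS-coded items are not components of any scene score.
3. Make the three-way comparison at admission, in the same patients.
4. If a reduced scene version is wanted, list its items in advance and label it as modified. Examples are ABC without FAST, or TASH limited to systolic blood pressure, heart rate and sex. Report it without the original TASH cut-off or probability table.

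Aligning the objective in the Protocol and SAP 2.1 is optional. The absence of a stated TASH threshold in SAP 5.2.3 is a separate point.

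Cost: up to two table cells and a few sentences, with no new data. The scene comparison of the three original scores is dropped, and the documents give no cut-off or probability table for a modified scene score.
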